12.5 Administrative Forms

Form	Appendix	Description
Participant Identification Code List	R	Used to document the participant's study identification number, name, and other identifying information. Stored separately from research records since it is the link between a study ID and participant's name.
Recruitment Log	C	Used to list participants screened; includes those who fail screening and those who are enrolled. Collects date, age, gender, race, care needs, relationship to PWD, Rural (Y/N), Agreed to participate, Reason for not enrolling, study ID
Phone Call Log	S	Used to log all phone call conversations/follow-ups
Study Personnel	T	Used to list contact information for all study personnel and their specific responsibilities
Heritage AAA Log		Used by the OC, who is an employee at Heritage Area Agency on Aging to log options counseling sessions
Research Log		Extensive Database with points of contact to track participants through the research process
Intervention Log		Database at University of Iowa where the OC-HE tracks options counseling sessions
EPIC		University of Iowa Electronic Medical Record where Care Plans will be uploaded or typed into the "notes"

		section
Participant Contact Form (from Clinic to Research Staff)	U	Used by clinicians to collect contact information about the potential participants so that the Research Manager can contact the interested potential participant
Participant Reimbursement Form	N	Used by the Interviewer to collect information about the participant so that the participant can be paid their \$20 incentive for each interview
Interview Script	V	Used by the interviewer to introduce the study, ask about adverse events, conduct the interview, and end the interview
Adverse Event Form	G	Used by the PI to report Adverse Events
Serious Adverse Event Form	H	Used by the PI to report Serious Adverse Events

12.6 Retention of Study Documentation

Study documents will be retained for a minimum of 5 years after the study has ended. After 5 years, paper copies and digital records of the study data will be destroyed.

13.0 Data Management

See Data Management Plan

13.1 External Data

N/A

13.2 Quality Control Procedures

The PI and Co-PI will be responsible for quality assurance, performing internal quality management of study conduct, data collection, documentation and completion.

Quality control (QC) procedures will be implemented as follows:

Informed consent --- While there is no signed consent document, the Research Manager will train interviewers on explaining the informed consent letter. Most interviews are not recorded until after the participant has given informed consent, so the Research Manager will not be able to listen to recordings. The Research Manager will attend 10% of the interviews with the student interviewer to assure that the interviewer is reading through the letter with accuracy and completeness. Feedback will be provided to the study team to ensure proper consenting procedures are followed.

Source documents and the electronic data --- Data will be initially captured on source documents (see **Section Error! Reference source not found.**, **Data Handling and Record Keeping**) and will ultimately be entered into the study database. To ensure accuracy, site staff will compare a representative sample of source data against the database, targeting key data points in that review. Interviewers will enter data directly into Qualtrics. Each session will be recorded and 20% of the interviews (21 interviews) will be re-entered and compared to check the accuracy of data entry.

Intervention Fidelity — Consistent delivery of the study interventions will be monitored throughout the intervention phase of the study. Procedures for ensuring fidelity of intervention delivery are described in **Section Error! Reference source not found., Interventionist Training and Tracking**.

Protocol Deviations — The study team will review protocol deviations on an ongoing basis and will implement corrective actions when the quantity or nature of deviations are deemed to be at a level of concern.

Should independent monitoring become necessary, the PI will provide direct access to all trial related sites, source data/documents, and reports for the purpose of monitoring and auditing by the sponsor/funding agency, and inspection by local and regulatory authorities.

13.2.1 Standard Operating Procedures

N/A

13.2.2 Data and Form Checks

The PI and the Project Manager will implement data quality control procedures through weekly team meetings to identify potential data anomalies such as:

- Missing data or forms
- Out-of-range or erroneous data
- Inconsistent and illogical dates over time
- Data inconsistency across forms and visits
- Not completing all fields of a "completed form" or no reason for missing data is provided

14.0 Concomitant Medications

N/A

15.0 Data and Safety Monitoring Activities

Given the nature of this study, single-site minimal risk trial, the [name] (PI) will be responsible for ensuring participants' safety on a daily basis. The Data and Safety Monitoring Board (DSMB) will act in an advisory capacity to monitor participant safety, evaluate the progress of the study, to review procedures for maintaining the confidentiality of data, the quality of data collection, management, and analysis.

The PI will meet with the research team weekly to conduct ongoing data and safety monitoring, and will meet bi-annually with the Data Safety Monitoring Board (DSMB) consisting of three external board members, Drs. [name], [name], and [name]. The PI will be informed of serious adverse events (SAEs) as soon as they occur and will notify the UI IRB and NIA within 24 hours of notification.

The DSMB will hold a minimum of two web-based conference calls per year (about two hours per call) to discuss protocols, progress of the intervention and research activities, and data and participant safety. The PI will prepare a Safety Report to be circulated prior to the scheduled call for DSMB members to review. The reports will contain information and analyses of study procedures, progress, and data and safety issues. The board members will review the study protocol and information presented in the report and will provide recommendations on recruitment, retention, quality control, and safety procedures while ensuring the confidentiality of the study participants and results. Through these activities, we will ensure that all

protocols are conducted in compliance with the AE and SAE guidelines and reports are sent to appropriate individuals including the University of Iowa IRB and the Program Officer at the NIH.

The content of the data and safety monitoring report will include: a brief summary of study organization, purpose and procedures, overall study status, participant enrollment and retention, reasons for non-participation, aggregated descriptive information of the participants, changes to study protocol, quality of collected data, status of data management, incidence of ADs/SAEs/unexpected problems and actions taken, and updated study timeline. The design of this study does not involve masking.

15.1 Study Completion and Close-Out Procedures

Close-out activities include:

- Verification that study procedures have been completed, data have been collected, and study intervention and supplies are returned to the responsible party or prepared for destruction.
- Assurance that all data queries have been completed.
- Assurance that correspondence and study files are accessible for external audits.
- Assurance that the study records are maintained and any relevant study information reported to the NIA.
- Assurance that the investigator will notify the IRB of the study's completion and store a copy of the notification.
- Preparation of a report summarizing the study's conduct.
- Participant notification of the study completion.

15.1.1 Participant Notification

Participants will receive a letter indicating that their participation in this study has ended. The letter will thank participants for their participation, let them know how they will be informed of the study results, and let them know who to contact the PI or Project Manager if they would like further information.

15.1.2 Confidentiality Procedures

Procedures

Participant confidentiality and privacy is strictly held in trust by the participating investigators, their staff, the DSMB, and the NIA. This confidentiality is extended to the data being collected as part of this study. Data that could be used to identify a specific study participant will be held in strict confidence within the research team. Personally-identifiable information from the study will not be released to any unauthorized third party without prior written approval of the sponsor/funding agency.

Privacy of the participants will be protected by only collecting personal information that is necessary for the purpose of the research. Data will be used only for research purposes. Names and personal information will be used only for logistic purposes such as scheduling interviews and mailing incentives after the completion of their surveys. The consent process will take place in a private location.

The DSMB, other authorized representatives of the NIA, or representatives of the Institutional Review Board (IRB) may inspect all documents and records required to be maintained by the investigator, including

but not limited to, medical records (office, clinic, or hospital) and other data collected in this study. The study site will permit access to such records.

Study participant research data, for purposes of statistical analysis and scientific reporting, will be transmitted to and stored in the secure online database. This will not include the participant's contact or identifying information. Rather, individual participants and their research data will be identified by a unique study identification number. The study data entry and study management systems used by clinical sites and by research staff will be secured and password protected. At the end of the study, all study databases will be de-identified and archived in the University of Iowa secure database.

Electronic records (computer files, electronic databases, etc.)

All research-related computer and audio files with identifying information will be kept on secure computer servers at the College of Public Health data center facility in a password protected folder accessed only by the study staff. The collegiate data center facility includes climate controlled redundant air cooling and humidity sensors, gigabit network bandwidth, enhanced electrical power, power conditioning, backup power via generator, and restricted access controls including two factor authentication with entry and exit logging. Server backups are run daily (business days) and preserved in a temperature stable and fireproof media safe. Monthly server backups are transported offsite for disaster recovery. The research staff responsible for entering, coding, cleaning, and verifying the transcripts and survey data will be trained in human subjects and confidentiality. Landmark Associates Incorporated (UI vendor ID 662416) is a UI approved vendor with a privacy and confidentiality agreement. Digital audiorecords and transcripts will be transferred via this company's secure file transfer program. Collegiate IT policies, plans, and procedures include Contingency and Disaster Recovery Plan, Incident Handling, Risk Assessment Management and Analysis, Facility Security Plan, Systematic Change Control Procedures, Data Destruction and Sanitization Guidelines, Server Monitoring and Audit Procedures, and Enterprise Password Policy.

- Name - [name]
- Title - IT Director
- University Job Classification - Faculty/Staff

Paper/hard copy records (hard copy surveys, questionnaires, case report forms, pictures, etc.)

The confidentiality of the participants and responses to interview questions will be protected throughout the study and after its completion. Each participant will be given an identification number for data management purposes and to ensure the confidentiality of his/her responses to interview and surveys. Any hard copy documents that may be produced during the study period will be stored securely in a locked cabinet in private offices of the study personnel. Only participant IDs without names will be indicated on hard copy surveys. Participants' names will not be used during transcription, data entry, and analysis, and will not appear in any report, paper, or presentation to ensure their privacy and confidentiality. Interviewers will be trained to not leave any study-related documents unattended between the time of interview and when materials are securely stored in the locked cabinets. Codes that can link participants to IDs will be stored in a secured locked cabinet separate from the identifying information in private offices, and will be accessible only by the trained study personnel including PI, project manager, research assistants, and interventionist. Audio files, transcripts, participant tracking, and interview responses will be kept in separate

databases using data encryption on the network of the College of Public Health with appropriate Access Control Lists restricting the files to those working directly on the project.

Measures Taken to Ensure Confidentiality of Data Shared per the NIH Data Sharing Policies

It is NIH policy that the results and accomplishments of the activities that it funds should be made available to the public (see <https://grants.nih.gov/policy/sharing.htm>). The PI will ensure all mechanisms used to share data will include proper plans and safeguards for the protection of privacy, confidentiality, and security for data dissemination and reuse (e.g., all data will be thoroughly de-identified and will not be traceable to a specific study participant). Plans for archiving and long-term preservation of the data will be implemented, as appropriate.

Certificate of Confidentiality

To further protect the privacy of study participants, the Secretary, Health and Human Services (HHS), has issued a Certificate of Confidentiality (CoC) to all researchers engaged in biomedical, behavioral, clinical or other human subjects research funded wholly or in part by the federal government. Recipients of NIH funding for human subjects research are required to protect identifiable research information from forced disclosure per the terms of the NIH Policy (see <https://humansubjects.nih.gov/coc/index>). As set forth in [45 CFR Part 75.303\(a\)](#) and [NIHGPS Chapter 8.3](#), recipients conducting NIH-supported research covered by this Policy are required to establish and maintain effective internal controls (e.g., policies and procedures) that provide reasonable assurance that the award is managed in compliance with Federal statutes, regulations, and the terms and conditions of award. It is the NIH policy that investigators and others who have access to research records will not disclose identifying information except when the participant consents or in certain instances when federal, state, or local law or regulation requires disclosure. NIH expects investigators to inform research participants of the protections and the limits to protections provided by a Certificate issued by this Policy.

APPENDIX A - ACRONYM GLOSSARY

Adverse Event (AE) – Any untoward or unfavorable medical occurrence in a clinical research study participant, including any abnormal sign (e.g. abnormal physical exam or laboratory finding), symptom, or disease, temporally associated with the participants' involvement in the research, whether or not considered related to participation in the research.

Case Report Form (CRF)/Reportable Event Form – A printed, optical, or electronic (eCRF) document designed to capture all protocol-required information for a study. Reportable Event Form is an online form filled out on the University of Iowa Institutional Review Board (Hawk IRB) site.

Code of Federal Regulations (CFR) - is an annual codification of the general and permanent rules published in the Federal Register by the executive departments and agencies of the Federal Government.

Data and Safety Monitoring Board (DSMB) –A group of individuals independent of the study investigators that is appointed by the NIA to monitor participant safety, data quality and to assess clinical trial progress.

Good Clinical Practice (GCP) – A standard for the design, conduct, performance, monitoring, auditing, recording, analyses, and reporting of clinical trials that provides assurance that the data and reported results are credible and accurate, and that the rights, integrity, and confidentiality of trial participants are protected.

Health Insurance Portability and Accountability Act (HIPAA) Privacy Rule – The first comprehensive Federal protection for the privacy of personal health information. The Privacy Rule regulates the way certain health care groups, organizations, or businesses, called covered entities under the Rule, handle the individually identifiable health information known as protected health information (PHI).

Heritage Area Agency on Aging (HAAA) - Heritage Area Agency on Aging (HAAA) is designated by the Iowa Commission on Aging to provide services and supports to older Iowans, adults with disabilities, and family caregivers in its seven-county region. [name] and [name], Executive Director, have a well-established and active collaborative relationship through multiple research endeavors, including the pilot study that served as a basis for this proposed study.

Institutional Review Board (IRB)/Independent Ethics Committee (IEC) – An independent body constituted of medical, scientific, and nonscientific members whose responsibility it is to ensure the protection of the rights, safety, and well-being of human subjects involved in a trial by, among other things, reviewing, approving, and providing continuing review of trials, protocols and amendments, and of the methods and material to be used to obtaining and documenting informed consent of the trial participant.

Manual of Procedures (MOP) – A “cook book” that translates the protocol into a set of operational procedures to guide study conduct. A MOP is developed to facilitate consistency in protocol implementation and data collection across study participants and clinical sites.

Options Counselor (OC) - Under Iowa Administrative Code [IAC231.64] HAAA is required to provide options counseling services. OCs meet with family and individuals to develop a person-centered plan to support independent living in their home and community as long as possible based on their current resources and available services. OCs provide transition support from medical to home environment,

ensuring essential supports at home and in the community by providing information to address current and anticipated needs of the family.

Options Counselor/Health Educator Intervention (OC-HE) - This intervention will consist of two components, Options Counseling (OC) and Health Education (HE). Family will receive standard OC services that include family assessment, counseling and provision of emotional support, access assistance, and development of independent-living plans (family action plans) using the Iowa's LifeLong Links database. In the HE component, family will receive post-diagnosis education. Interventions will be ongoing and flexible to meet the needs of the individual family.^{2,3} OC-HE will conduct initial assessment to determine educational needs (2 weeks later), and will conduct 5 monthly follow-up calls to adjust the care plans and provide educational components appropriate at each point. This will create direct links between the medical clinics, HCBS, and family

Principal Investigator (PI) - The individual with primary responsibility for achieving the technical success of the project, while also complying with the financial and administrative policies and regulations associated with the award. Although Principal Investigators may have administrative staff to assist them with the management of project funds, the ultimate responsibility for the management of the sponsored research award rests with the Principal Investigator.

Quality Control (QC) – The internal operational techniques and activities undertaken within the quality assurance system to verify that the requirements for quality of trial related activities have been fulfilled (e.g., data and form checks, monitoring by study staff, routine reports, correction actions, etc.)

Safety Officer (SO) - The Safety Officer is an independent individual, usually a clinician, who performs data and safety monitoring activities in low-risk, single site clinical studies. The Safety Officer advises NIA Program Director regarding participant safety, scientific integrity and ethical conduct of a study.

Serious Adverse Event (SAE) – Any adverse event that:

- Results in death
- Is life threatening, or places the participant at immediate risk of death from the event as it occurred
- Requires or prolongs hospitalization
- Causes persistent or significant disability or incapacity
- Results in congenital anomalies or birth defects
- Is another condition which investigators judge to represent significant hazards

Standard Operating Procedure (SOPs) – Detailed written instructions to achieve uniformity of the performance of a specific function across studies and patients at an individual site.

APPENDIX B – ELIGIBILITY SCREENING

Participants must meet all of the inclusion and none of the exclusion criteria in order to be eligible to participate in the study.

Each box must be checked “yes” for a participant to be eligible for the study:

Yes No

- Are you 18 years of age or older as of today?
- Are you a family member/caregiver of someone who has been diagnosed with Alzheimer’s/dementia within the past 24 months?
- Do you have any cognitive limitations that may prevent you from giving informed consent?
- Do you have access to a phone line where you can receive monthly phone calls?

“No” must be checked for the question below for a participant to be eligible for the study:

- Does the PWD currently reside at a facility/institution of care?

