5.1 Screening and Eligibility Criteria

Assuming some people may not meet the inclusion criteria, we anticipate screening around 138 potential participants including women and minorities to reach target enrollment size.

Participants will be screened verbally, with the research assistant asking whether the participant meets the inclusion criteria (*see Eligibility Screening Tool in Appendix B*). Participants must meet *all* of the inclusion criteria in order to be eligible to participate in the study. Once the individual has been determined to be eligible, research assistant will schedule a time with the individual to consent to the study. After the individual has received the consent letter and the research assistant has read through the document with the individual, and the individual agrees to participate, the he/she will be considered enrolled. The participant will not be randomized until after completing the baseline survey. For every eligible potential participant, the research assistant will collect information about their age, gender, race, physical disability status

(whether the person needs assistance completing study-related tasks such as consenting and participating in interviews), whether the potential participant agreed to participate, and the reason for declining using the recruitment log. This will provide information on the extent to which our program is reaching caregivers of diverse backgrounds and to inform ways to increase reach to under-represented groups. Being included in the recruitment log does not indicate that the individual is necessarily enrolled in the study. Women and minority groups are encouraged to participate in this study. Because of the demographic characteristic of the patient population at the UIHC, primarily white, we will attempt to reach out to minority participants as much as we can to increase diversity. The control group will have the same inclusion/exclusion criteria.

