One of the eligibility criteria, diagnosis of dementia, will be determined based on the clinical diagnosis made by physicians in our collaborating clinics. Once potential participants are identified by the clinical staff, research staff will conduct other assessments related to screening to determine eligibility using the above-described eligibility screening tool, before enrolling the participant. Screening and enrollment procedures will be conducted by one or two research staff to minimize variability. If more than one staff will engage in these procedures, two staff members will discuss procedures and criteria in detail to minimize variability in these procedures.

Individuals who exhibit high levels of anxiety based on the GAD-7 scale¹ (score of 10 or higher) in baseline will be advised to seek clinical care. These individuals will have an option to discontinue in this study.

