5.3 Eligibility Criteria

Inclusion Criteria

Family Participants/Caregivers

1. Over the age of 18
2. Self-reported family member/caregiver of someone who has been diagnosed with Alzheimer's/dementia within the past 6 months
3. Lives in the state of Iowa or the PWD lives in Iowa
4. No cognitive limitations that prevent them from consenting or participating in interviews (Evaluation to Sign an Informed Consent Document for Research, a form provided by the University of Iowa Institutional Review Board shown in Appendix E)
5. Access to necessary resources for participating in monthly phone calls

Staff participants

1. During the time of the study, worked as staff at the UIHC Neurology, Memory Disorder, or Psychiatry clinic and took a part in this study; or Served in an administrative role at the Heritage Area Agency on Aging during this project period or delivered intervention for this study
2. Over the age of 18

Exclusion criteria:

1. Those residing at care settings at the time of the recruitment
2. Families/caregivers of those diagnosed as predementia or mild cognitive impairment
3. Individuals with cognitive impairments and physical limitations that limit ability to make informed decisions or participate in interviews.

Individuals who exhibit high levels of anxiety based on the GAD-7 scale¹³ (score of 10 or higher) in baseline will be advised to seek clinical care. These individuals will have the option to discontinue in this study.

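### The Appendix B screening form uses a 24-month diagnosis window where section 5.3 sets 6 months; its cognitive-limitations item also sits in the wrong answer block

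*Protocol*

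**What the plan says.** Section 5.1 of the protocol describes the procedure: "Participants will be screened verbally, with the research assistant asking whether the participant meets the inclusion criteria", and it points to Appendix B as the tool. It goes on to leave the dementia diagnosis itself to the physicians in the collaborating clinics, after which "research staff will conduct other assessments related to screening to determine eligibility using the above-described eligibility screening tool". Section 12.2 has the form read to the potential participant before any materials are handed over, and then kept in the participant folder.

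The form opens with a general rule: "Participants must meet all of the inclusion and none of the exclusion criteria in order to be eligible to participate in the study". Four questions follow that must all be answered yes: age, a diagnosis of "dementia within the past 24 months", "Do you have any cognitive limitations that may prevent you from giving informed consent", and access to a phone line. A single question must be answered no: whether the person with dementia lives in a care facility.

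Section 5.3 has "dementia within the past 6 months" in inclusion 2, "No cognitive limitations that prevent them from consenting or participating in interviews" in inclusion 4, and "Individuals with cognitive impairments and physical limitations that limit ability to make informed decisions or participate in interviews" in exclusion 3.

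Section 2.0, the Participants text of section 5.0 and the first script in Appendix V all give 6 months. The Recruitment text of section 5.0 also gives 6 months, but counts it from the start of the study. The SAP calls the patients newly diagnosed and gives no number of months.

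**The concern.** The screening form is where a written criterion becomes a decision about a person. Its diagnosis item reads naturally, so nothing in the wording would prompt a research assistant to notice that the window differs from section 5.3. The cognitive item is different: taken literally it is unworkable, so staff would be likely to correct for it.

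What is at stake is the description of the population. Both documents present the families as newly diagnosed, and the protocol gives that term two meanings. Randomizing a caregiver who fits only the form's longer window would be a deviation of a kind that section 11.0 names explicitly, namely randomizing someone who is not eligible. The screening records that can be seen would not reveal it. The form records only yes or no, and the recruitment log (section 12.5 and Appendix C) has no field for the date of diagnosis.

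**Working it through.** There is no statistical figure to reproduce. The check sets the texts side by side.

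**Diagnosis window**

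| Place in protocol | Window | Counted from |
|---|---|---|
| Section 2.0 | 6 months | not stated |
| Section 5.0, Participants | 6 months | not stated |
| Section 5.0, Recruitment | 6 months | beginning of the study |
| Section 5.3, inclusion 2 | 6 months | not stated |
| Appendix V, first script | 6 months | not stated |
| Appendix B, screening form | 24 months | not stated |

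Difference: 24 − 6 = 18 months. Ratio: 24 / 6 = 4.

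With time counted back from screening, the two rules give:

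| Time since diagnosis | Form item | Inclusion 2 |
|---|---|---|
| Up to 6 months | pass | pass |
| More than 6, up to 24 months | pass | fail |
| More than 24 months | fail | fail |

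The middle row is the conflict.

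**Reference date.** Suppose the beginning of the study means the August 2019 enrolment start planned in section 2.0. A diagnosis made 6 months before that date would be 6 + 13 = 19 months old at the planned end of recruitment in September 2020. That is outside inclusion 2 counted back from screening, but inside the form's 24 months. The length and the starting point of the window therefore both need settling.

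**Cognitive item.** A caregiver who is eligible on these points truthfully answers yes on age, yes on diagnosis, no on cognitive limitations and yes on phone access. That is 3 of the 4 required yes answers, so the printed rule fails this caregiver. A caregiver who has such a limitation passes the item. Both results reverse inclusion 4 and exclusion 3. A fault in text extraction is unlikely, because the No instruction refers to one question and exactly one follows it.

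**Is the difference a recorded change?** The modification log in Appendix X has no entries, so nothing shown marks 24 months as deliberate.

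**Where the dates might be found.** The baseline interview (Appendix L) is not shown. Section 12.5 lists a research log but not its fields. Section 6.1 states access to the medical record, but names only MoCA and use of medical services as data collected from it. Any of these might hold the diagnosis date; the documents do not say.

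**The case against.** The strongest reply is that the form is not the main gate. Under section 5.0 the clinical teams find patients in the electronic record on a 6-month window. Section 5.1 gives the diagnosis to clinic physicians and keeps the form for the other assessments. The phone script tells callers 6 months, and the form's first line invokes every criterion. Five places say 6 months and one line says 24. The cognitive item is a drafting slip that staff would notice at the first screening, and inclusion 4 calls for a separate capacity evaluation, printed as Appendix W.

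Most of this stands, and it limits the exposure. It does not remove the conflict. The sentence about physicians states no time window. The form's first line conflicts with the items printed beneath it, so it cannot settle which one governs.

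A reader might infer more than the documents support:

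- *Ineligible caregivers were enrolled.* No enrolment data are given, and referral already works on 6 months.
- *The reversed item admitted impaired caregivers or shut out eligible ones.* That requires staff to apply it literally, against its evident intent and the capacity evaluation.
- *The Recruitment text replaces inclusion 2 with a window fixed at study start.* The same sentence keeps eligibility as a separate condition. It leaves the reference date unclear and does no more.
- *The arms were selected differently.* Section 5.1 applies the same criteria to both groups, and section 8.0 places randomization after the baseline assessment.

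**Conclusion.** The concern holds as an internal contradiction in a form that is used to decide eligibility, and it should be fixed. The main fault is the window: 24 months against 6. The misplaced cognitive item is a genuine error but probably has almost no practical effect.

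The number of participants affected cannot be estimated, because the documents give no distribution of diagnosis dates. The consequence that can be shown is narrow: possible undetected eligibility deviations, and a sample description that rests on an unsettled definition.

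This rests on two assumptions: that Appendix B as printed is the form that was used, and that inclusion 2 is counted back from screening, which is its natural reading but is not stated. The documents do not establish which window was intended, and none is preferred here.

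**What to change.** - Reconcile the diagnosis window to one length and one reference date in sections 2.0, 5.0 (Participants and Recruitment) and 5.3 and in Appendices B and V. If 24 months was a deliberate change, record it in the Appendix X log.
- Move the cognitive-limitations question to the block that must be answered no, and make that instruction plural.
- Check enrolled participants' diagnosis dates against the reconciled criterion, using whichever record holds them: the baseline interview, the research log, or the medical record if the approved access covers it.
- Report any deviations, and state the window actually applied wherever the sample is called newly diagnosed, including in the SAP.

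Recruitment was planned to end by September 2020 and the SAP is dated January 2022. If enrolment has closed, the date check and the disclosure are the parts that still matter.

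The text changes amount to a one-page form revision, matching edits and an IRB modification. The effort for the record check depends on where the dates are held. It should be small if the baseline interview or research log has them, and larger if further access to the medical record must be approved.
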